1/21/20	5.3	Removed question about caregiver missing work/activities
1/21/20	5.6	Removed study calendars and thank-you cards for participants
3/2/20	3.0	Amended eligibility to include stage IVa esophageal patients
3/26/20	3.0	Removed patient inclusion criterion "receiving first course of radiation therapy"
5/28/20	Co-Is	[name] added as a Co-I
5/28/20	4.0	Consent to be obtained remotely by phone or Redcap during COVID-19
5/28/20	5.3	Intervention sessions 2 & 3 delivered by phone during COVID-19
5/28/20	5.63	Symptom screening and masking for COVID-19 symptoms
7/23/20	4.0	Opt-out period for remote consent changed to 2 days
7/23/20	4.0	In-person consent will be used if remote consent is not feasible
10/2/20	4.0	Removed unique identifying code from remote consent process
12/4/20	5.3	Expanded time period for intervention session 2 to 3 rd -4 th week of XRT
2/23/21	5.3	Expanded time period for intervention session 1 to first 10 days of XRT
2/23/21	5.53	Added letter reminder between T3 and T4 surveys
12/6/21	3.0	Amended eligibility for NSCLC to include stage II (excluding SBRT)
1/5/22	Co-Is	[name] removed as a Co-I
4/5/22	5.2, 5.3	Added COST-FACIT, MOS Social Support, and Health insurance surveys
12/1/22	Co-Is, 1.0, 2.0, 3.0, 4.0, 5.1, 5.4, 5.54, 6.1	Extension protocol changes: added [name], MetroHealth, increased sample size, qualitative interviews, and analysis for new sub-aims.
6/11/24	Co-Is	Removed [name] and added [name]
3/13/25	PIs	Removed [name] and added [name]

TABLE OF CONTENTS

1.0	INTRODUCTION.....	6
1.1	Overview	6
1.2	Background and Rationale.....	6
2.0	OBJECTIVES	13
3.0	RESEARCH SUBJECT SELECTION.....	13
4.0	RESEARCH SUBJECT ENTRY.....	15
5.0	STUDY DESIGN AND METHODS	17
5.1	Design/Study Type	17
5.2	Selection of Instruments	17
5.3	Description of Intervention.....	20
5.4	Data Collection.....	22
5.5	Description of Study Process.....	24
5.6	Adverse Reactions and Their Management.....	25
6.0	STATISTICAL ANALYSIS.....	27
7.0	REFERENCES.....	31
8.0	APPENDICES.....	38

INTRODUCTION

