We estimate, based on the annual Cancer Registry data, that 131 patients with stage I, II, III rectal, anal, and esophageal cancers; stage III NSCLC; and stage I-IV A/B HNC will be receiving radiation therapy at the three study sites of the Cancer Center. Approximately 10% of these patients will not meet our eligibility criteria (e.g., no family CG), resulting in 118 potential participants annually. Based upon our current pilot study, *Building Family CG Skills Using a Simulation-Based Intervention for Care of Patients with Head and Neck Cancer*, we expect a CG refusal rate of 40%. Therefore, we project to enroll 71 CGs per year or 5 per month. We plan to enroll subjects for 36 months, resulting in an enrollment of 180 subjects over the course of the study. We will allow for a 10% dropout rate, resulting in 162 subjects for the final analysis. The estimated 10% attrition rate is based on a current caregiver intervention study in the Cancer Center, in which the rate is 9.7% (NR015464, [name] PI).

While 40% is a high refusal rate, it is consistent with other intervention studies that aimed to enroll patient-caregiver dyads.^{2,3,90} In addition, the use of incentives has been found to reduce the refusal rate in this CG population, and thus, we will offer a \$100 incentive to all CGs for participation in the study. We will also seek IRB approval to collect additional information from CGs who refuse, including whether the CG is working and/or providing care to other individuals, which were common reasons for refusal in the pilot study. Lastly, we will monitor the refusal rate monthly. If the refusal rate is greater than 40% for more than 4 months, we will consider revising our strategies and seek other sites. We will offer a \$40 incentive to all patients for participation in the study.

For the extension period, with the increased number of study sites we project to enroll 6 caregivers per month. We plan to enroll subjects for an additional 16 months, resulting in 96 subjects over the course of the extension project. We project that the parent study will enroll a total of 148 subjects. Adding the 96 subjects in the extension project will result in a total sample size between the parent study and extension project of 244. With an estimated dropout rate of 12%, the sample for the final analysis will be 214 dyads.

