Power. Analyses for Aim 4 to examine moderating effects will be primarily exploratory in nature, since it is well-recognized that power for testing interaction effects is not high in trials that are powered to detect main effects, as is the case here.¹¹² When testing interaction of a binary factor occurring with frequency 0.5, power is 0.86 to detect an interactive effect size of 1.0 SDs (e.g., an intervention effect of 1.0 in one subgroup and an effect of 0.0 in the other), using a 2-sided test, significance level 0.05.

Aim 4a: Analyses for Aim 4a will examine if the SDH variables moderate the relationship between the intervention and caregiver outcomes. Effects of potential modifiers of the treatment effect will be examined by including terms for the SDH modifier by treatment interaction effect in the basic ANCOVA model used to test the primary hypothesis. The increase in enrollment from the extension study will provide additional power, as it is well-recognized that power for testing interaction effects is not high in trials that are powered to detect main effects, as was the case with the parent study. When testing interaction of a continuous SDH modifiers and the treatment, power is 0.81 to detect an interactive effect size of 0.40 standard deviations (SD) using a 2-sided test, significance level 0.05, for those measures that will be available in all subjects (e.g. Ohio Opportunity Index). For SDH measures that will only be available in the 96 extension study participants, we will be able to detect an interactive effect size of 0.59 at the same power and significance levels.

Aim 4b: Qualitative interviews will be audio recorded and transcribed, then verified for accuracy by research staff. Any identifiable information will be removed from transcripts, and each will be assigned a

study number. Deidentified data will be analyzed with NVIVO software using thematic analysis. First, the research team, including the PI, will read and reread 5 transcripts to develop a codebook using an inductive approach. Then, all transcripts will be coded by the research team using NVIVO to organize the data. Additional codes, and subsequently categories of codes will be identified. Clusters of categories converged into themes. Each transcript will be read and coded by three members of the research team for interrater reliability.

Aim 5

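### Aim 4a's 0.59 SD figure assumes the added social-determinant measures exist only in the 96 extension caregivers, but those surveys predate the extension, and the figure allows for no dropout

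*Combined protocol and SAP*

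**What the plan says.** - **Section 6.0, Aim 4a, power.** Two figures are given for a continuous modifier. For measures held on all subjects, with the Ohio Opportunity Index as the example, "power is 0.81 to detect an interactive effect size of 0.40 standard deviations (SD) using a 2-sided test, significance level 0.05". The second figure begins "For SDH measures that will only be available in the 96 extension study participants" and continues "we will be able to detect an interactive effect size of 0.59 at the same power and significance levels". The measures meant by the second figure are not named.
- **Section 6.0, Aim 4a, analysis.** Each modifier-by-treatment term is added to the ANCOVA model of the primary hypothesis. Nothing restricts this by enrolment period.
- **Section 3.0, Projected Enrollment.** "We project that the parent study will enroll a total of 148 subjects". For the extension, "We plan to enroll subjects for an additional 16 months, resulting in 96 subjects over the course of the extension project". The total is 244, and 12% dropout leaves 214 for analysis.
- **Amendment log.** The 4/5/22 row, for sections 5.2 and 5.3, reads "Added COST-FACIT, MOS Social Support, and Health insurance surveys". The 12/1/22 row, "Extension protocol changes", includes "increased sample size, qualitative interviews, and analysis for new sub-aims". It does not list 5.2, where the surveys are described, but it does list 5.4, which holds Table 4.
- **Current methods text.** Section 5.2 presents health insurance, social support and financial toxicity as three additional measures, with no limit to the extension. Table 4 schedules MOS at T2 and COST at T2 and T4, also without a limit. Section 5.1 says the only design change in the extension is the qualitative interview.

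**The concern.** The power statement ties some measures to the extension cohort. The rest of the document introduces the only candidate measures earlier and applies them to everyone. If the surveys ran from about April 2022, parent-study caregivers enrolled before the extension also have them, and 96 is not the number with data.

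The two adjacent power figures also appear to rest on different bases, one before dropout and one after, so they cannot be compared as printed.

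What is at stake is the accuracy of the stated power for these moderator tests, where the plan itself says power is not high and offers the extension partly as a source of more. There is also a smaller risk: the power sentence is the only text that says who has these measures, so an analyst could take it as the definition of the analysis set.

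**Working it through.** **Model.** Interaction slope per 1 SD of the modifier, 1:1 allocation (assumed for Aim 4a; the Aim 1 power text uses equal arms), residual SD of 1. Then SE = 2/√N and power ≈ Φ(effect/SE − 1.96). The t version uses a noncentral t with N − 4 degrees of freedom.

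**Step 1: reproduce the plan's figures.**

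| N | Effect (SD) | SE | Power, normal | Power, t | Simulation, random modifier |
|---|---|---|---|---|---|
| 96 | 0.59 | 0.204 | 0.824 | 0.816 | 0.796 |
| 84 | 0.59 | 0.218 | 0.771 | 0.762 | 0.734 |
| 214 | 0.40 | 0.137 | 0.833 | 0.830 | 0.823 |
| 244 | 0.40 | 0.128 | 0.878 | 0.875 | 0.867 |

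The stated power is 0.81. The 0.59 SD figure reproduces at 96, that is, before dropout. The 0.40 SD figure fits 214 (after dropout) and not 244.

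**Step 2: check the basis by ratio.** Detectable effects scale as 1/√N, so this check does not depend on the model's SD.
- The plan's ratio is 0.59/0.40 = 1.475.
- Mixed basis: √(214/96) = 1.493.
- Both before dropout: √(244/96) = 1.594.
- Both after dropout: 96 × 0.88 = 84.5, and √(214/84.5) = 1.59.

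The plan's pair matches the mixed basis.

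**Step 3: put 0.59 SD on the after-dropout basis.** Scaling gives 0.59 × √(96/84) = 0.63 SD. Solving directly at power 0.81 gives 0.619 (normal) or 0.627 (t).

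**Step 4: count the window.** From 4/5/22 to 12/1/22 is 240 days, and 240/30.4375 = 7.9 months. The documents give no accrual for this window, so the rate is an assumption. The rate of 4.11 per month is 148/36, 5 is the planned parent rate, and 3.5 and 6 are outer bounds (6 is the planned extension rate).

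| Rate per month | Added | Enrolled with 96 | After 12% dropout | Detectable at power 0.81 (t) |
|---|---|---|---|---|
| 3.5 | 27.6 | 123.6 | 108.8 | 0.549 |
| 4.11 | 32.4 | 128.4 | 113.0 | 0.539 |
| 5 | 39.4 | 135.4 | 119.2 | 0.524 |
| 6 | 47.3 | 143.3 | 126.1 | 0.509 |

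**Step 5: visit timing.** MOS is taken at T2, and COST at T2 and T4. T2 falls at about 6 to 8 weeks and T4 20 weeks later, at about 26 to 28 weeks. If the surveys were also given to caregivers already enrolled on 4/5/22, the parent-study addition at 4.11 to 5 per month becomes about 38 to 49 for a T2 measure and 57 to 72 for COST at T4. The count therefore differs by measure.

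**Step 6: net direction.** The two errors pull in opposite directions. They cancel when the number analysed is 96, which needs 96/0.88 = 109 enrolled, or about 13 more than 96. Above that, 0.59 SD is pessimistic. If no parent-study caregiver has the measure, it is optimistic and about 0.63 SD applies.

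**The case against.** The strongest reply is that 96 is an availability assumption in a power sentence and not an analysis rule. The Aim 4a analysis text excludes no one. The section plans an intent-to-treat analysis and multiple imputation of missing predictors to keep partial information, and a statistician following it would use every caregiver with the measure. This stands. A reader might infer that the plan leaves out about a quarter of usable caregivers. The documents do not support that: there is no exclusion, and the share itself (25% to 29% at 4.11 to 5 per month, 22% to 33% at 3.5 to 6) rests on assumed accrual.

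Three further points also stand:
- The measures are not named in the power sentence, so identifying them as COST, MOS and insurance is an inference. It is the natural one, since no other candidate is described. It is weakest for insurance, which is not clearly a continuous modifier.
- The log gives amendment dates, not dates of first use, and the document gives no date of first enrolment into the extension. That parent-study caregivers enrolled in the window completed the surveys is likely but not documented.
- If 96 is too low, the statement is conservative on that count. Nothing is biased and the primary endpoint is untouched.

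What the reply does not answer is that the availability claim conflicts with sections 5.1 and 5.2 and Table 4, or that the two detectable effects use different dropout bases. The log is used here only for dates; no superseded wording is set against current text.

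**Conclusion.** The point holds as an error in stated availability and power, not as a stated exclusion.

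The basis mismatch follows from the plan's own figures: 0.59 SD reproduces only at 96 before dropout, and on 84 analysed its power is about 0.76 (0.73 to 0.77 by method). It assumes only that the 12% dropout applies equally to the extension cohort.

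The undercount is probable but not proven. It assumes that the 4/5/22 amendment date approximates first use and that the parent study was still enrolling until about 12/1/22, which its forward-looking projection of 148 suggests. With both corrections, the detectable interaction is about 0.52 to 0.54 SD at the central accrual rates and 0.51 to 0.55 SD over the wider range. Those figures count by enrolment date and would shift with visit timing for MOS and COST.

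The consequence is modest. The plan calls the Aim 4 moderator analyses mainly exploratory, and the primary analysis is unaffected. The correction is worth making because it is cheap and settles the analysis set in advance.

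**What to change.** 1. In Aim 4a, state that each social-determinant moderator test uses every randomised caregiver with that measure, whether enrolled in the parent or the extension period.
2. Name the measures that are not held on all subjects, and replace 96 with the actual count for each measure and time point.
3. Restate the detectable interaction for the number analysed, on the same after-dropout basis as the 0.40 SD figure.
4. If a measure truly was collected only in the extension, say so and reconcile sections 5.1 and 5.2 and Table 4 with it. The figure for that measure is then about 0.63 SD on 84 analysed.

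The cost is a few sentences in section 6.0 and one database count per measure. No new data are needed.

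### Aim 4a: the extension-only detectable interaction (0.59 SD at 0.81 power) counts all 96 enrolled caregivers with no dropout, while the adjacent all-subjects figure fits the post-dropout sample

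*Combined protocol and SAP*

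**What the plan says.** **Aim 4a (Section 6).** Two detectable interactions are given for continuous modifiers. For measures held on all subjects, "power is 0.81 to detect an interactive effect size of 0.40 standard deviations (SD) using a 2-sided test, significance level 0.05". For measures that will "only be available in the 96 extension study participants, we will be able to detect an interactive effect size of 0.59", power and significance level are said to be the same.

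**Sample sizes (Section 3.0, Projected Enrollment).** The extension recruits 6 caregivers a month for 16 months, "resulting in 96 subjects over the course of the extension project". For the parent study, "We project that the parent study will enroll a total of 148 subjects". These add to 244. "With an estimated dropout rate of 12%, the sample for the final analysis will be 214 dyads".

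**Aim 4 (Section 6).** "When testing interaction of a binary factor occurring with frequency 0.5, power is 0.86 to detect an interactive effect size of 1.0 SDs", illustrated as "an intervention effect of 1.0 in one subgroup and an effect of 0.0 in the other". No N is given there. The summary at the end of the Aim 5 text says that power for the other aims was assessed at the Aim 1 sample, n = 162.

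**The concern.** In Section 3.0, 96 is a count of people enrolled. The analysed sample for the extended trial is obtained only after 12% dropout. In the Aim 4a text the same 96 appears as the basis of a detectable effect, with no dropout taken off, next to a figure that seems to rest on a post-dropout sample.

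Aim 4a was added with the extension, and the plan cites the added power for interactions as a benefit of the larger enrolment. The extension-only figure governs any moderator that exists only for extension participants. If it is too favourable, a null moderation result for such a measure will be read as more informative than it is.

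**Working it through.** **Inputs.** Two-sided 0.05, stated power 0.81, and effects of 0.40 and 0.59 SD (Aim 4a). Power 0.86 for 1.0 SD with a binary modifier at frequency 0.5 (Aim 4). 96, 148 and 244 enrolled, 12% dropout, 214 analysed (Section 3.0). n = 162 at 81 per arm (Aim 1).

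**Formulas.** With 1:1 allocation and a unit residual SD, the standard error of a treatment-by-modifier term is 2/√N for a continuous modifier in SD units. It is 4/√N for a binary modifier split 50/50. Power is taken from the noncentral t with N − 4 degrees of freedom. The normal approximation is Φ(effect/SE − 1.96).

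**Step 1: reproduce the plan's 0.59.** At N = 96, 0.59 × √96 / 2 = 2.89. Power is 0.824 (normal) or 0.816 (t). A simulation with a randomly drawn modifier gives 0.798. The stated 0.81 is reproduced.

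**Step 2: apply the plan's dropout.** 96 × 0.88 = 84.5, so about 84. This is the same rounding down that turns 244 × 0.88 = 214.7 into 214. At N = 84, 0.59 × √84 / 2 = 2.70. Power is 0.772 (normal), 0.762 (t) or 0.733 (simulation). The effect detectable at 0.81 power is 0.619 (normal) or 0.627 (t), about 0.63 SD.

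**Step 3: check the all-subjects figure.** At N = 214, 0.40 × √214 / 2 = 2.93. Power is 0.833 (normal), 0.830 (t) or 0.819 (simulation). This is consistent with the stated 0.81. At the enrolled 244 it would be 0.875 (t).

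**Step 4: a check that does not depend on the SD scale.** At equal power and alpha, the squared ratio of two detectable effects is approximately the inverse ratio of their sample sizes. (0.59/0.40)² = 2.18. With rounding, the range runs from (0.585/0.405)² = 2.09 to (0.595/0.395)² = 2.27.

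| Pairing | Ratio | In range? |
|---|---|---|
| 214 / 96 (after / before dropout) | 2.23 | yes |
| 214 / 84 (both after) | 2.55 | no |
| 244 / 96 (both before) | 2.54 | no |

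The two Aim 4a figures therefore fit a post-dropout N paired with a pre-dropout N.

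**Step 5: Aim 4's 0.86.**

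| N | 1.0 × √N / 4 | Power (normal) | Power (t) |
|---|---|---|---|
| 148 | 3.04 | 0.860 | 0.856 |
| 162 | 3.18 | 0.889 | 0.885 |
| 214 | 3.66 | 0.955 | 0.954 |

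The stated 0.86 corresponds to an N of about 148 (normal) to 150 (t). At 162 it is about 2.5 points too low.

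**The case against.** **Baseline adjustment.** Aim 4a places the interaction in the ANCOVA model of the primary analysis, and Aim 1 assumes a baseline correlation of 0.50 for anxiety. Crediting that (SE multiplied by √0.75), 84 analysed caregivers would have about 0.87 power for 0.59 SD, above the stated 0.81. This is true for anxiety under those assumptions, but it does not account for the plan's figure. The same credit gives about 0.91 at 96 and 0.92 at 214 (for 0.40 SD), not 0.81. The stated figures appear to be unadjusted, and on that footing the dropout is missing.

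**The true N may not be 84.** The change log dates the COST, MOS Social Support and insurance surveys to 4/5/22, about eight months before the extension entry of 12/1/22. Sections 5.2 and 5.4 do not restrict these measures to extension participants. Some parent-study caregivers may therefore have them, but the number is not given. As an assumption, 4 to 5 enrolled per month over those eight months adds 32 to 40. That makes 128 to 136 enrolled and about 112 to 119 analysed at 12% dropout, with power of about 0.87 to 0.89 for 0.59 SD. About 95 analysed would be enough for 0.81. This objection stands: 84 follows from the plan's own wording and is not an established count.

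**Aim 4 is labelled primarily exploratory**, and its 0.86 errs on the cautious side. This also stands, and it makes that point minor.

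**Stronger readings that the documents do not support.** A reader might infer that none of the Aim 4 and 4a power figures follows from an analysed sample; the 0.40 SD figure does. A reader might also infer that 0.86 was computed from the parent study's projected 148; the number fits, but the plan never says so. Nor is Aim 4a the sole purpose of the extension, which also added a site and qualitative interviews.

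**Conclusion.** The concern holds for one of the two Aim 4a figures. On the plan's premise that some measures exist only for the 96 extension enrollees, 0.59 SD at 0.81 power omits the 12% dropout applied elsewhere. With about 84 analysed, power at 0.59 SD is about 0.76, a loss of some 5 points, or the detectable interaction at 0.81 power is about 0.63 SD.

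This rests on three assumptions: the overall 12% holds within the extension, no parent-study caregiver contributes these measures, and no gain from baseline adjustment is credited. The first two are open. The third matches how the stated figures behave.

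The Aim 4 figure is a traceability fault with no loss of power: 0.86 stated against 0.885 at 162. The primary analysis and the total sample size are unaffected.

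**What to change.** 1. **Aim 4a, extension-only.** Restate the figure on the post-dropout N and name that N. On the plan's present wording this is about 84 analysed, with about 0.63 SD detectable at 0.81 power or power of about 0.76 at 0.59 SD. Say that no baseline adjustment is credited, if that is so.
2. **Which caregivers have the measures.** Check whether parent-study caregivers surveyed after 4/5/22 also have COST, MOS or insurance data. If they do, replace the 96 with the expected analysed N for each measure and recompute.
3. **Aim 4.** State the N and correct the power to about 0.885 at 162, or about 0.95 if the text is updated to 214.
4. **Aim 4a, all subjects.** Leave 0.40 SD as it is. Naming 214 beside it would make the basis plain.

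The cost is a few sentences in Section 6 and a count from the survey records. One stated figure may become slightly less favourable. Design, recruitment and analysis do not change.
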